To address *Aims 1 and 2*, the modelling approach will vary depending on the nature of the outcome. PrEP initiation will be modelled using a probit model (preferred to estimate risk factors for common outcomes) with individual-level covariates as fixed effects; when time-dependent or visit-specific covariates are included in the analysis of cumulative initiation (for *Aim 2*) we will shift to a mixed-effects setting with random effects around individual participants. PrEP continuation will be examined using similar approaches; in addition, we will use time-to-event methods to estimate factors associated with time to loss (non-continuation) among women having initiated PrEP. PrEP persistence will be modelled using mixed effects probit models as above and generalized estimating equations to examine the marginal effect of individual-level covariates on persistence during the study. Throughout, robust estimates of standard errors will be used.

For each outcome, covariates in the multivariable models will be selected a priori using directed acyclic graphs; the main exposures of interest include: age (<25 vs. >25 years old), pregnancy status (by trimester and pregnant vs. postpartum), relationship status (married/cohabiting vs. not) and substance use (vs. none). We will explore associations within subgroups of participants using interaction terms in predicting outcomes involving these four covariates in particular. Throughout the analysis of outcomes in the PrEP cascade, losses of patients at early stages are highly informative about outcomes later in the cascade. To specifically address this, we will perform further bias analyses with inverse probability of censoring weighting in addition to complete case analyses. We will also use multiple imputation via chained equations for missing data [83] to examine the potential impact of missing data.

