#### ***Methods:***

Relevant approaches may include:

- (1) Inclusion of all participants in data evaluation regardless of intervention group,
- (2) Tabulation of descriptive statistics for key variables (including missing observations),
  - a. Key variables include: age, education, relationship status, partner's HIV status, IPV, depression, substance use, PrEP knowledge, STI status, persistence to PrEP at v2 and beyond, SAEs, birth outcomes
- (3) Histograms, quantile plots of baseline levels and follow-up measures and changes in those measures.

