#### 4. Table and Figure Templates

Outline tables and figures that will be produced for the analysis. This will include all analyses. Tables and figures for the paper will be constructed separately.

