**Table 1. HIV risk factors associated with PrEP uptake in HIV-uninfected pregnant women (N=XXX)**

	Person time on PrEP (n=x)		Person time not on PrEP (n=y)		Crude HR (95% CI)	Adjusted HR (95% CI)
	n	%	N	%		
Age (median and IQR)						
Age <25 years						
Age >=25 years						
Primigravida						
Knew about PrEP						
Ready to start PrEP today (Agree + Strongly Agree)						
Intended to get pregnant						
Married or cohabiting						
More than 1 sex partner						
STI+ diagnosis (chlamydia, gonorrhoea, and/or trichomonas vaginalis)						
Reported depression or anxiety in pregnancy (EPDS <13 score)						
HIV+ partner						
Partner HIV status unknown						
Reported IPV in past year						
Reported alcohol/drug use in past year						

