#### Birth outcomes

	PrEP user (n)	%	PrEP non-user (n)	%	Comment
Number of active participants					
Number of women still pregnant					
Number of Births					
Number of Live Births					
Number of Birth abnormalities					
Still births					
Miscarriage					
Other					

Monthly and quarterly report templates (can be by PrEP status for our DSMB and other analyses)

Table 1: Monthly enrolment information for participants

Description	N for this month	% for this month	Cum. total (for study)	% Cum. total	Comments
Enrolment Status					
Total Screened					
Ineligible					
Refusals					
Enrolled participants					
Withdrawals (total N=X)					
Study withdrawals					Monthly PIDs:
Censored from study					
Lost to follow up (90+ days without a visit and not contactable)					
Total					
PrEP Status of Study participants (total N=X)					
On PrEP ( $\geq 18$ yrs)					

On PrEP (16-17 yrs)					
Not on PrEP (18 $\geq$ yrs)					
Not on PrEP (16-17 yrs)					
Total					
Visit attendance					
Attended Refill visit (v1.1)					
Attended v2					
Not on PrEP (v2- subset of above row)					
AE and SAE reporting					
AEs reported ( $\geq$ 18 yrs)					
AEs resolved ( $\geq$ 18 yrs)					
AEs reported (16-17 yrs)					
AEs resolved (16-17 yrs)					
SAEs (denominator= total enrolments)					
Birth outcomes					
Normal					
Adverse (& reason)					
Total births					
STI diagnosis					
CT					
NG					
TV					
CT/NG					
CT/TV					
TV/NG					
CT/NG/TV					
Total					
Referrals					

IPV					
EPDS (depression)					
AUDIT					
DUDIT					
HIV results at Baseline					
HIV negative					
Ag					
Ab					
Ag/Ab					
Total Tested Participants					
HIV results at visit 2+					
HIV negative					
Ag					
Ab					
Ag/Ab					
Total tested					

Abnormal laboratory results (creatinine)	
Unanticipated problems	
Protocol Deviations	
Quality Management	

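### The depression row in the SAP's Table 1 shell appears to have its inequality reversed (EPDS below 13), and nothing else in the plan defines the variable

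*Combined protocol and SAP*

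**What the plan says.** SAP section 4 (Table and Figure Templates) gives a Table 1 shell titled "HIV risk factors associated with PrEP uptake in HIV-uninfected pregnant women". It has n and % columns for person-time on and off PrEP, then a crude and an adjusted hazard ratio. One row is "Reported depression or anxiety in pregnancy (EPDS <13 score".

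Depression or the EPDS appears in two other relevant places in the SAP:

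- Section 2.1 (Preliminary evaluation of data, Methods) includes depression among the key variables to be tabulated: "partner's HIV status, IPV, depression, substance use, PrEP knowledge, STI status". It gives no cut-off.
- The Referrals block of the monthly report template has the line "EPDS (depression". It gives no cut-off, range or direction.

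The protocol's list of survey measures does not name the EPDS, and the SAP's baseline characteristics template has no depression row. The Table 1 label is therefore the only place where a numerical definition of the variable appears.

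**The concern.** The label and the definition in this row point in opposite directions. The label names women who have depression or anxiety. On the instrument's usual scoring, the bracketed rule picks out women with few symptoms.

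The rest of the table supports reading the label as the intended group. Other single-category rows name the state being counted, for example "Reported IPV in past year", a positive STI result, an HIV-positive partner, or alcohol or drug use.

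With no derivation elsewhere, a programmer who follows the shell has only this rule to code. The output would give little warning: the hazard ratio would look plausible and the p-value would be the one expected. A reader taking the row at its label would draw the opposite conclusion about how depression relates to PrEP uptake.

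**Working it through.** No sample size, power, alpha or event figure depends on this row, so the plan has no figure to reproduce. The check has two parts.

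**1. Is the variable defined anywhere else?**

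| Place | What it gives |
|---|---|
| SAP section 4, Table 1 shell | EPDS below 13, labelled as depression or anxiety |
| SAP section 2.1, key variables | Depression named; no cut-off |
| SAP monthly template, Referrals | EPDS named with depression; no cut-off |
| SAP baseline characteristics template | No depression row |
| Protocol, survey measures | EPDS not named |

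Nothing confirms or corrects the printed inequality. The scoring direction is not stated in the documents either. That a higher score means more symptoms is taken here as a general property of the instrument.

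**2. What would literal coding do?**

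Let D = 1 if EPDS ≥13 and D′ = 1 if EPDS <13. Among women with a score, D′ = 1 − D.

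- *Percentage.* If a proportion p scores 13 or more, the row as printed shows 1 − p. The documents give no value for p. For an assumed range: p = 0.05 gives 1 − 0.05 = 95%; p = 0.10 gives 90%; p = 0.20 gives 80%; p = 0.30 gives 70%.
- *Hazard ratio.* Replacing D by 1 − D changes the log hazard ratio from b to −b, so HR becomes 1/HR. For assumed values: 1/0.5 = 2.00; 1/0.8 = 1.25; 1/1.25 = 0.80; 1/2.0 = 0.50.
- *p-value.* The estimate changes sign and its standard error does not, so the two-sided p-value is the same. The fitted model is the same in other respects, so the other covariates' estimates do not move.

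A simulated Cox model confirmed this (n = 1200, assumed 15% scoring ≥13, assumed true HR 0.5, one adjustment covariate):

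| Coding | HR | 95% CI |
|---|---|---|
| EPDS ≥13 | 0.490 | 0.395 to 0.608 |
| EPDS <13 | 2.041 | 1.645 to 2.532 |

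The second line is the reciprocal of the first: 1/0.490 = 2.041, 1/0.608 = 1.645 and 1/0.395 = 2.532. The p-value was the same in both fits, about 9 × 10⁻¹¹.

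**The case against.** The strongest reply is that this is one row label in an empty shell, not a derivation rule, and a slip of the pen is the likeliest explanation. The SAP says of these shells that "Tables and figures for the paper will be constructed separately". The monthly template contains a similar harmless slip, where the adult age band for women not on PrEP has its inequality sign on the wrong side of the number. The scoring direction comes from outside the documents. Even if the row were coded literally, it would still print its own definition, and an implausibly high percentage might be caught by the distribution checks in SAP section 2.1.

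Much of this stands, and it limits what can be claimed. A reader might infer three stronger things that the documents do not support:

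- *That women are being misclassified and the association is inverted.* No code, derivation or result is shown. Inversion follows only if the label is coded literally and the output is then read as depression.
- *That a named Aim 2 factor is affected.* Depression is not among the individual-level factors listed for Aim 2. It is not among the four main exposures either ("the main exposures of interest include: age (<25 vs. >25 years old), pregnancy status", then relationship status and substance use), and it is not a listed subgroup.
- *That referral counts are wrong.* The Referrals line carries no cut-off, and nothing links it to the Table 1 label.

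The template defence does not remove the point. The section introduces the shells as the tables to be produced for the analysis; only the paper's own tables are set apart. With no other definition in the plan, the printed cut is what a programmer would follow.

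**Conclusion.** The point holds as a correction to one row. On the EPDS's usual scoring, the inequality in the Table 1 depression row appears to be reversed, and the plan contains nothing that would put it right. Coded as printed, the row would show the complement percentage and the reciprocal of the intended crude and adjusted hazard ratios.

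The conclusion rests on two conditions: that higher EPDS scores mean more symptoms, which the documents do not state, and, for any effect on results, that the label is coded literally. The percentages and hazard ratios used as illustration are assumed. The effect is confined to this row: the primary cascade outcomes, the main exposures, the sample size and power statement, and the row's p-value would not change.

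**What to change.** Relabel the Table 1 row as EPDS ≥13, with <13 as the reference group. This keeps the plan's own threshold: ≥13 is the exact complement of the printed cut, so no new cut-off is introduced. Add one derivation line to the SAP giving the cut-off, the scoring direction and the reference category. Use that single coded variable wherever depression is tabulated or modelled, namely the section 2.1 key-variable summaries and the Table 1 hazard ratios.

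The change concerns the analysis variable only and sets no referral rule. It costs one inequality sign, one line of text and the matching code, with no extra data collection, no effect on sample size and no statistical downside.

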**Table 2. Continuation, persistence and outcomes in those on PrEP (n=XXX)**

	On PrEP (n=XXX)		Change from last quarter
	n	%	
Returned for 1 month visit			
Persistence (self reported taking PrEP 5+ days of last 7 days)			
Persistence (self reported taking PrEP 25+ days of last 30 days)			
Returned for 3 month visit			
Persistence (self reported taking PrEP 5+ days of last 7 days)			
Persistence (self reported taking PrEP 25+ days of last 30 days)			
Returned for 6 month visit			

Persistence (self reported taking PrEP 5+ days of last 7 days)				
Persistence (self reported taking PrEP 25+ days of last 30 days)				
Returned for 9 month visit				
Persistence (self reported taking PrEP 5+ days of last 7 days)				
Persistence (self reported taking PrEP 25+ days of last 30 days)				
Returned for 12 month visit				
Persistence (self reported taking PrEP 5+ days of last 7 days)				
Persistence (self reported taking PrEP 25+ days of last 30 days)				
Returned for 15 month visit				
Persistence (self reported taking PrEP 5+ days of last 7 days)				
Persistence (self reported taking PrEP 25+ days of last 30 days)				
Returned for 18 month visit				
Persistence (self reported taking PrEP 5+ days of last 7 days)				
Persistence (self reported taking PrEP 25+ days of last 30 days)				
Continuation on PrEP at v3 (defined as not missing >1 Study visit in those on PrEP)				
Continuation on PrEP at v4				
Continuation on PrEP at v5				
Continuation on PrEP at v6				
Continuation on PrEP at v7				

#### Adverse events and serious adverse events (PrEP use defined as taking PrEP in last 30 days)

	PrEP users (N)	%	PrEP non-users (N)	%	Comment
Adverse event reported (n=# of events and # of participants)					
Type of events					
Serious adverse event reported (n= # of events)		% over # of participants in study			
Type of events					
HIV testing					

HIV ab+					
HIV ag+					
HIV ag/ab+					

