Health outcomes and adverse events	Any side-effects, change in creatinine clearance, any negative maternal or neonatal outcomes (for mother and infant) compared by PrEP use/non-use	Electronic provider log (REDCap)	Weekly and quarterly
Infant growth outcomes	Measure infant weight, length, z-score and any adverse events in infants compared by PrEP use/non-use	Electronic provider log (REDCap)	Weekly and quarterly

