#### ***Methods/Approach:***

- (1) Study flow figure (see Continuation Flowcharts)
- (2) Number screened per week and month (target= 18 per week, 72 per month) vs number enrolled
  - a. The projected sample size for the study is 1200 women enrolled until 12-months postpartum (estimated mean of 18-months follow-up).
- (3) Subjects initiating PrEP compared to those who do not
  - a. Estimated that 60% of women (n=720) will initiate PrEP during the study period (versus approximately 40% who will not).
- (4) Continuation and persistence by group
  - a. Assumed that approximately 75% of women on PrEP (n=540) will continue on PrEP at 12-months (defined as not missing >1 study visit among women on PrEP);
  - b. Assumed that 70% of those retained in care (n=378) will adhere to PrEP during at-risk periods.
- (5) Final completion rates
  - a. Compare final number of participants who enroll in study, who initiate PrEP, who are retained in care, and who adhere to PrEP to sample sizes needed to yield 80% power (i.e., n=1200, 720, 540, 378, respectively).
- (6) Number of subjects in analysis data sets
  - a. Consider number of participants that will potentially be excluded from analyses because of withdrawal from study, missing data on key covariates or outcomes, etc.

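### The SAP safety table states a whole-cohort denominator for serious adverse events in a PrEP user/non-user layout, so its percentage is not either group's risk

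*Combined protocol and SAP*

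**What the plan says.** The adverse event template in SAP section 4 (Table and Figure Templates) has a count column and a percentage column for PrEP users, and the same pair for non-users. Its title fixes the grouping: "PrEP use defined as taking PrEP in last 30 days". The SAE row is labelled "Serious adverse event reported (n= # of events", and the note on its percentage reads "over # of participants in study". In the text as extracted, that note stands in the user percentage cell and the non-user percentage cell is empty. The ordinary adverse event row above it asks for both events and participants.

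Other parts of the plan call for a comparison between groups:

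- Protocol section 2, objective 1(4), asks for the proportion of women with adverse events among those on PrEP and among those not on PrEP.
- SAP Table 1 (Study measures for Aim 1) lists "any negative maternal or neonatal outcomes (for mother and infant) compared by PrEP use/non-use".
- SAP section 2.6 plans tabulation by group, count and person-time analyses, and a count of subjects by their highest grade of event. It gives no denominator for an SAE percentage.

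The monthly report template, also in section 4, has the row "SAEs (denominator= total enrolments". Its columns are monthly and cumulative totals, not PrEP groups, although the templates may be split by PrEP status for the DSMB and other analyses.

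**The concern.** A percentage in a user column, set beside one in a non-user column, will be read as the risk in each group. If both are divided by the whole cohort, each is the group's risk multiplied by its share of the cohort, so the larger group looks worse even when the risks are equal. If only the user column is divided by the whole cohort, users look safer than they are. Either way the display does not answer objective 1(4).

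The numerator is a separate problem. Events over people is not a proportion: a woman with three SAEs contributes three to the numerator and one to the denominator. At stake is how SAEs by PrEP use are read in a cohort of pregnant women and adolescents, for whom the protocol has set up an independent DSMB.

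**Working it through.** **Inputs from SAP section 2.2 (Description of study process).**

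- Cohort: "The projected sample size for the study is 1200 women enrolled until 12-months postpartum".
- Initiators: "Estimated that 60% of women (n=720) will initiate PrEP during the study period".
- Continuing: "Assumed that approximately 75% of women on PrEP (n=540) will continue on PrEP at 12-months".

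These reproduce: 1200 × 0.60 = 720, leaving 480 non-initiators; 720 × 0.75 = 540, leaving 1200 − 540 = 660.

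**Assumptions.** The documents give no SAE rate. I take the same true risk r in both groups, with r = 5% as the illustration and 2% to 10% as the range, and one event per affected woman. I also take all 1200 women as falling into one group or the other.

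**Formulas.** Let N = 1200, U = users and V = N − U.

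- Reading A, whole cohort in both columns: U·r/N against V·r/N. Displayed ratio = U/V.
- Reading B, whole cohort in the user column only and own group in the other: U·r/N against r. Displayed ratio = U/N.
- Own group in both columns: r against r. Ratio = 1.0.

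**Results at r = 5%.**

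| Split | Reading A | Reading B | Own group |
|---|---|---|---|
| 720 / 480 | 36/1200 = 3.0% v 24/1200 = 2.0%; ratio 1.50 | 3.0% v 24/480 = 5.0%; ratio 0.60 | 5.0% v 5.0%; ratio 1.0 |
| 540 / 660 | 27/1200 = 2.25% v 33/1200 = 2.75%; ratio 0.82 | 2.25% v 33/660 = 5.0%; ratio 0.45 | 5.0% v 5.0%; ratio 1.0 |

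**Dependence on the assumed risk.** Under reading A at 720/480, r = 2% gives 1.2% v 0.8% and r = 10% gives 6.0% v 4.0%. The ratio is 1.50 each time, because r cancels. Under reading A the artefact disappears only at an exact 600/600 split.

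**Effect on a real difference.** If the risk in users were truly doubled, the 720/480 split would display 2 × 720/480 = 3.0 under reading A and 2 × 720/1200 = 1.2 under reading B. The same true effect can therefore look exaggerated or nearly absent, depending on how the programmer reads one note.

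**The case against.** **What the note may mean.** The author may only have been telling the programmer to count people rather than events. The column headers carry a group N, the note sits in one cell, and table extraction may have displaced it. That reading is possible, and it is why the size is given for more than one reading. But the words name the study, not the group, and no other place in the plan supplies a group denominator for the SAE percentage.

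**What the template governs.** Section 4 says that tables for the paper will be constructed separately. SAP section 2.6 already plans tabulation by group, person-time methods and subject counts by highest grade, so repeated events in one woman are partly dealt with there. The protocol (Internal monitoring) has all serious maternal and infant events reported to the DSMB and the ethics committee, and counts stand beside the percentages. All of this stands and limits the consequence. It does not make the stated percentage right.

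**Stronger readings the documents do not support.**

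- A reader might infer that the artefact reverses over time, giving a false alarm early and false reassurance later, especially by setting 720 against 378. But 378 is the number expected to adhere during at-risk periods, not the number who took any PrEP in the last 30 days, and 720 is cumulative initiation over the study. These figures are not a time course of user numbers.
- A reader might infer that the monthly report repeats the error. It does not as it stands: total enrolments is a valid denominator for a pooled row. A problem would arise only if that row were split by PrEP status with the denominator left unsplit.

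**Conclusion.** The point holds for the SAE row of the safety table. Taken literally, its denominator and its event-based numerator do not give each group's SAE risk, and the row conflicts with objective 1(4) and with the by-group comparison in SAP Table 1 and section 2.6. Under equal risk the displayed ratio at the planned 720/480 split is 1.5 or 0.60, according to where the whole-cohort denominator is applied; at 540/660 with the cohort in both columns it is 0.82. The true ratio is 1.0.

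These figures rest on using the SAP's initiation and continuation numbers in place of the number of last-30-day users, which the documents do not project. They do not rest on any particular SAE risk. This is a reporting-template fault that should be corrected before by-group safety tables are produced. It does not show that the underlying safety data or the person-time analysis are wrong.

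**What to change.** In the SAE row of the SAP section 4 safety table, replace the percentage note with two lines for each PrEP group:

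1. women with at least one SAE, over women in that group;
2. SAE events, over person-time in that PrEP category, with the intervals already planned in section 2.6.

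Because last-30-day use can change between visits, add one sentence saying when a woman is classified for line 1. In line 2, assign each event to the category the woman was in when it occurred.

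In the monthly report, keep total enrolments for the pooled SAE row. State that, if the row is split by PrEP status, the denominator becomes the enrolments or person-time in that same category.

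Cost: a few lines of SAP table wording and a small programming change. No new data are needed.

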#### Birth outcomes

	PrEP user (n)	%	PrEP non-user (n)	%	Comment
Number of active participants					
Number of women still pregnant					
Number of Births					
Number of Live Births					
Number of Birth abnormalities					
Still births					
Miscarriage					
Other					

Monthly and quarterly report templates (can be by PrEP status for our DSMB and other analyses)

Table 1: Monthly enrolment information for participants

Description	N for this month	% for this month	Cum. total (for study)	% Cum. total	Comments
Enrolment Status					
Total Screened					
Ineligible					
Refusals					
Enrolled participants					
Withdrawals (total N=X)					
Study withdrawals					Monthly PIDs:
Censored from study					
Lost to follow up (90+ days without a visit and not contactable)					
Total					
PrEP Status of Study participants (total N=X)					
On PrEP ( $\geq 18$ yrs)					

On PrEP (16-17 yrs)					
Not on PrEP (18 $\geq$ yrs)					
Not on PrEP (16-17 yrs)					
Total					
Visit attendance					
Attended Refill visit (v1.1)					
Attended v2					
Not on PrEP (v2- subset of above row)					
AE and SAE reporting					
AEs reported ( $\geq$ 18 yrs)					
AEs resolved ( $\geq$ 18 yrs)					
AEs reported (16-17 yrs)					
AEs resolved (16-17 yrs)					
SAEs (denominator= total enrolments)					
Birth outcomes					
Normal					
Adverse (& reason)					
Total births					
STI diagnosis					
CT					
NG					
TV					
CT/NG					
CT/TV					
TV/NG					
CT/NG/TV					
Total					
Referrals					

IPV					
EPDS (depression)					
AUDIT					
DUDIT					
HIV results at Baseline					
HIV negative					
Ag					
Ab					
Ag/Ab					
Total Tested Participants					
HIV results at visit 2+					
HIV negative					
Ag					
Ab					
Ag/Ab					
Total tested					

Abnormal laboratory results (creatinine)	
Unanticipated problems	
Protocol Deviations	
Quality Management	

